4.2 EXCLUSION CRITERIA

1. current DSM-IV diagnosis of any psychoactive substance dependence other than cocaine or nicotine
2. have a DSM-IV axis I psychiatric disorder or neurological disease or disorder requiring ongoing treatment and/or making study participation unsafe
3. have cognitive impairment due to non-substance related factors (e.g., history of stroke, transient ischemic attacks, mental retardation, epilepsy, head injury)
4. significant current suicidal or homicidal ideation
5. medical conditions contraindicating levodopa/carbidopa or ropinirole pharmacotherapy (e.g., evidence of any movement disorder, clinically significant pulmonary disease, cardiovascular disease, liver or kidney disease, seizure disorder)
6. taking CNS active concomitant medications
7. taking medications known to have significant drug interactions with the study medication(s) (e.g., CYP P-450-2D6 inhibitors, such as tamoxifen, iron salts, pyridoxine, monoamine oxidase inhibitors, phenothiazines, selegiline, anesthetics)
8. currently or recently (last 3 months) treated for substance use or another psychiatric condition
9. having conditions of probation or parole requiring reports of drug use to officers of the court
10. impending incarceration
11. pregnant or nursing for female patients
12. inability to read, write, or speak English
13. having plans to leave the immediate geographical area within 3 months
14. unwillingness to sign a written informed consent form.

5. STRATEGIES FOR RECRUITMENT AND RETENTION

The study will be conducted at the outpatient Treatment Research Clinic (TRC), a component of the Department of Psychiatry and Behavioral Sciences Center for Neurobehavioral Research on Addictions (CNRA). Participants will be non-hospitalized, self-referred persons who call in response to various advertising strategies, including newspaper/newsletter articles and announcements, public service announcements on television and radio, notices mailed to local professionals, city-wide billboards, and posters located throughout the local community.

6. STUDY INTERVENTIONS

6.1 STUDY DRUG #1

Levodopa. The drug, levodopa (L-3,4-dihydroxyphenylalanine), is a dopamine precursor. It is combined with a decarboxylase inhibitor, which prevents the levodopa from being metabolized in the peripheral circulation before it reaches the brain. Levodopa with the decarboxylase inhibitor carbidopa (trade name Sinemet), is a highly effective symptomatic treatment for the motor disability of Parkinson's disease, a condition characterized by loss of dopaminergic function primarily in the substantia nigra. Similar to other agents used in the treatment of Parkinson's disease and also studied as potential cocaine medications (e.g., amantadine, selegiline), levodopa increases extracellular dopamine and dopamine transmission. Levodopa/carbidopa pharmacotherapy is safe and well tolerated in cocaine dependent outpatients.

Participants assigned to a levodopa/carbidopa condition will receive the sustained release formulation (Sinemet CR), titrated according to schedule below. The dosage and titration schedule have been used in our previous levodopa trials

6.2 STUDY DRUG #2

Ropinirole. The drug, ropinirole, is a DA (primarily type D₂ and D₃) receptor agonist used in the treatment of Parkinson's disease. Preliminary studies suggest that ropinirole is safe, and may reduce cocaine use. In an open-label trial (Meini et al., 2008), 39 subjects with cocaine dependence received ropinirole at 1.5 mg/day for 12 weeks. Average rates of benzoyllecgonine-positive urines decreased from 90.2% at baseline to 17.8% at week 6. Twelve subjects achieved sustained cocaine abstinence for up to 10 weeks.

Participants assigned to a medication combination condition will also receive ropinirole in the extended-release formulation (REQUIP XLTM), with a one-week dose titration schedule to reach fixed dose levels of 2.0 mg/d or 4.0 mg/d, depending on study condition. These doses were chosen based on a previous study of ropinirole in cocaine dependence and dosage titration recommended for Parkinson's disease to minimize risk of side effects (REQUIP XLTM prescribing information) (see titration schedule, below).

6.3 PLACEBO

Placebo. We will use a matched placebo procedure for maintaining the blind. Placebo capsules will be identical in size, color, coating and shape to the active study medication. All placebos will be packed in capsules with riboflavin added and contained in a blister pack affixed with patient instructions.

Participants in all conditions will take the same number of capsules at the same scheduled times (morning/evening) per day throughout treatment. Participants will take one matching placebo twice per day, at the same time they take their active study medication.

6.4 MEDICATION DISPENSING

At each clinic visit (MWF) subjects will be administered the medication at the dispensing window and given take-home doses for intervening days. Riboflavin (50mg) will be added to the medication (and placebo) capsules and used as a marker to monitor compliance. We will use a double-dummy method involving a matched placebo for each of the two medications. Placebo capsules will be identical in size, color, coating and shape. Participants in all conditions will take the same number of capsules at the same scheduled times (morning/evening) per day throughout treatment. Participants in the single medication condition will take one matching placebo twice per day, at the same time they take their active study medication. Participants in the placebo group will take two matching placebos twice per day. This method, along with additional strategies used in our clinic to protect the integrity of blindness, will be applied.

Placebo + placebo

	Wk1	Wk2	Wk3	Wk4	Wk5	Wk6	Wk7	Wk8	Wk9	Wk10
L-dopa/carb	0	0	0	0	0	0	0	0	0	0
ropinirole	0	0	0	0	0	0	0	0	0	0
Total										
I-dopa/carb	0mg									
ropinirole	0 mg									
Morning dose	1 capsule placebo ; 1 capsule placebo									
Evening dose	1 capsule placebo ; 1 capsule placebo									
Total pills	4	4	4	4	4	4	4	4	4	4
	Run-up			Maintenance						Run-down

Comments: High dose condition (l-dopa/carbidopa + ropinirole 4 mg/d) has option to hold ropinirole dose at 2 mg/d if tolerability issues. Blood pressure monitoring at every clinic visit.

Levodopa-carbidopa 800/200 mg/d + placebo

	Wk1	Wk2	Wk3	Wk4	Wk5	Wk6	Wk7	Wk8	Wk9	Wk10
L-dopa/carb	200/50 x 2	400/100 x 2	400/100 x 2	400/100 x 2	400/100 x 2	400/100 x 2	400/100 x 2	400/100 x 2	400/100 x 2	200/50 x 2
ropinirole	0	0	0	0	0	0	0	0	0	0
Total L-dopa/carb	400/100 0 mg	800/200 0 mg	400/100 0 mg							
Morning dose	1 capsule containing 2-200/50 tablets; 1 capsule placebo									
Evening dose	1 capsule placebo; 1 capsule placebo	1 capsule containing 2-200/50 tablets; 1 capsule placebo	1 capsule containing 2-200/50 tablets; 1 capsule placebo	1 capsule containing 2-200/50 tablets; 1 capsule placebo	1 capsule containing 2-200/50 tablets; 1 capsule placebo	1 capsule containing 2-200/50 tablets; 1 capsule placebo	1 capsule containing 2-200/50 tablets; 1 capsule placebo	1 capsule containing 2-200/50 tablets; 1 capsule placebo	1 capsule containing 2-200/50 tablets; 1 capsule placebo	1 capsule placebo; 1 capsule placebo
Total pills	4									
	Run-up				Maintenance					Run-down

Levodopa-carbidopa 800/200 mg/d + ropinirole 2 mg/d

	Wk1	Wk2	Wk3	Wk4	Wk5	Wk6	Wk7	Wk8	Wk9	Wk10
L-dopa/carb	200/50 x 2	400/100 x 2	400/100 x 2	400/100 x 2	400/100 x 2	400/100 x 2	400/100 x 2	400/100 x 2	400/100 x 2	200/50 x 2
ropinirole	0 mg	2 mg	0 mg							
Total L-dopa/carb	400/100 0 mg	800/200 2 mg	400/100 0 mg/d							
Morning dose	1 capsule containing 2-200/50 tablets; 1 capsule containing placebo	1 capsule containing 2-200/50 tablets; 1 capsule containing placebo	1 capsule containing 2-200/50 tablets; 1 capsule containing placebo	1 capsule containing 2-200/50 tablets; 1 capsule containing placebo	1 capsule containing 2-200/50 tablets; 1 capsule containing placebo	1 capsule containing 2-200/50 tablets; 1 capsule containing placebo	1 capsule containing 2-200/50 tablets; 1 capsule containing placebo	1 capsule containing 2-200/50 tablets; 1 capsule containing placebo	1 capsule containing 2-200/50 tablets; 1 capsule containing placebo	1 capsule containing 2-200/50 tablets; 1 capsule containing placebo
Evening dose	1 capsule placebo; 1 capsule placebo	1 capsule containing 2-200/50 tablets; 1 capsule 2mg requip	1 capsule containing 2-200/50 tablets; 1 capsule 2mg requip	1 capsule containing 2-200/50 tablets; 1 capsule 2mg requip	1 capsule containing 2-200/50 tablets; 1 capsule 2mg requip	1 capsule containing 2-200/50 tablets; 1 capsule 2mg requip	1 capsule containing 2-200/50 tablets; 1 capsule 2mg requip	1 capsule containing 2-200/50 tablets; 1 capsule 2mg requip	1 capsule containing 2-200/50 tablets; 1 capsule 2mg requip	1 capsule placebo; 1 capsule placebo
Total pills	4									
	Run-up				Maintenance					Run-down

Levodopa-carbidopa 800/200 mg/d + ropinirole 4 mg

	Wk1	Wk2	Wk3	Wk4	Wk5	Wk6	Wk7	Wk8	Wk9	Wk10
L-dopa/carb	200/50 x 2	400/100 x 2	400/100 x 2	400/100 x 2	400/100 x 2	400/100 x 2	400/100 x 2	400/100 x 2	400/100 x 2	200/50 x 2
ropinirole	0	2 mg	4 mg	2 mg						
Total										
L-dopa/carb ropinirole	400/100 0 mg	800/200 2 mg	800/200 4 mg	400/100 2 mg						
Morning dose	1 capsule containing 2-200/50 tablets; 1 capsule containing placebo	1 capsule containing 2-200/50 tablets; 1 capsule containing placebo	1 capsule containing 2-200/50 tablets; 1 capsule containing placebo	1 capsule containing 2-200/50 tablets; 1 capsule containing placebo	1 capsule containing 2-200/50 tablets; 1 capsule containing placebo	1 capsule containing 2-200/50 tablets; 1 capsule containing placebo	1 capsule containing 2-200/50 tablets; 1 capsule containing placebo	1 capsule containing 2-200/50 tablets; 1 capsule containing placebo	1 capsule containing 2-200/50 tablets; 1 capsule containing placebo	1 capsule containing 2-200/50 tablets; 1 capsule containing placebo
Evening dose	1 capsule placebo; 1 capsule placebo	1 capsule containing 2-200/50 tablets; 1 capsule 2mg requip	1 capsule containing 2-200/50 tablets; 1 capsule 4mg requip	1 capsule containing 2-200/50 tablets; 1 capsule 4mg requip	1 capsule containing 2-200/50 tablets; 1 capsule 4mg requip	1 capsule containing 2-200/50 tablets; 1 capsule 4mg requip	1 capsule containing 2-200/50 tablets; 1 capsule 4mg requip	1 capsule containing 2-200/50 tablets; 1 capsule 4mg requip	1 capsule containing 2-200/50 tablets; 1 capsule 4mg requip	1 capsule placebo; 1 capsule 2mg requip
Total pills	4	4	4	4	4	4	4	4	4	4
	Run-up				Maintenance					Run-down

6.5 NON MEDICATION INTERVENTIONS

Cognitive Behavioral Therapy (CBT). Participants will receive individual CBT in 50-minute weekly sessions. Including CBT will allow us to replicate the behavioral therapy condition that proved most efficacious when used previously in our levodopa and citalopram trials. Cognitive-behavioral therapy is based on the model of relapse proposed by Marlatt and Gordon. The model regards coping skills training as the key component for avoiding drug use and preventing relapse. Skills training techniques include (1) self-monitoring and functional analysis of situational factors associated with craving or drug use; (2) learning alternative non-drug responses for handling high risk situations; and (3) general lifestyle modifications (e.g., increasing pleasant drug-free events, anger management, interpersonal skills, general problem-solving). An unpublished treatment manual written by [name] (PI) and implemented in several completed studies, closely parallels the treatment content found in other published CBT manuals. All CBT sessions will be audio-taped for adherence and competence ratings using recommended procedures done in all our treatment studies. Weekly supervision will be held by a designated clinical supervisor who will provide feedback to keep CBT delivery consistent and prevent drift.

Prize-based attendance CM (Contingency Management). During Treatment, for each visit attended, subjects will earn a draw from the attendance voucher “fishbowl”. The fishbowl has 500 slips in it. Many of the slips have a value of \$1, some have a value of \$25, one slip is worth \$100, and half of the slips just say “Good Job”. Subjects will earn 5 bonus draws for each week in which all 3 visits in a week (that is, Monday, Wednesday, and Friday) are attended. Vouchers for the \$25 and \$100 value slips will be given in the form of a gift card. For the \$1 slips, \$1 in cash or a voucher will be given.

The schedule of fishbowl draws for attendance and compliance is shown in Table 1 below.

Table 1. Draw Schedule

Week	1			2			3			4			5		
Visit	1	2	3	4	5	6	7	8	9	10	11	12	13	14	15
Draws	1	1	1	2	2	2	3	3	3	4	4	4	5	5	5
Bonus			5			5			5			5			5
Total Draws	1	1	6	2	2	7	3	3	8	4	4	9	5	5	10
Week	6			7			8			9			10		
Visit	16	17	18	19	20	21	22	23	24	25	26	27	28	29	30
Draws	6	6	6	7	7	7	8	8	8	9	9	9			
Bonus			5			5			5			5			
Total Draws	6	6	11	7	7	12	8	8	13	9	9	14			
Week	11			12			13			Total: 180 Draws					
Visit	31	32	33	34	35	36	37	38	39	Total: 180 Draws					
Draws										Total: 180 Draws					
Bonus										Total: 180 Draws					
Total Draws										Total: 180 Draws					

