1. ABSTRACT/STUDY DIAGRAM

Most cocaine dependent patients suffer from deficits in cognitive function that, if left untreated, predict poor outcome.

Purpose: The present study investigates a pharmacotherapeutic intervention designed to improve cocaine treatment success by combining medications that act simultaneously on dopamine, the brain system that is critically associated with chronic cocaine use and cognitive functions. **Procedures:** Treatment with levodopa/carbidopa plus ropinirole (tested at two doses) will be compared to levodopa/carbidopa alone, and placebo. Measurement of performance on behavioral/cognitive measures of decision-making, behavioral inhibition, reward motivation, and attentional bias will be conducted at treatment entry and at repeated time points during the 10-week treatment. It is hypothesized that treatment with levodopa/carbidopa + ropinirole will produce superior outcomes in terms of reduced cocaine use and increased treatment retention and that these effects will occur indirectly via improved performance on observed cognitive mechanisms. **Course of Study:** Eligible cocaine dependent patients will be randomized equally to one of four medication conditions. Outpatient treatment will last 10 weeks and consist of thrice-weekly clinic visits. The behavioral therapy platform for this trial will consist of weekly cognitive behavioral therapy (CBT). The primary outcome measure will be weekly mean proportion of cocaine non-use days. Secondary endpoints will include abstinence rates during the last 2 weeks of treatment, time in study, and medication compliance. **Enrollment:** This project requires a final intent-to-treat sample size of 200 subjects. To obtain this sample, we expect to conduct phone screens on ~ 640 individuals, of whom 320 (50%) will qualify, enroll, and start intake. Of the 320 who start intake, we expect that 200 (~60%) will complete intake and be randomized into the ITT sample. Based on these projections and recruitment rates achieved during our previous levodopa studies, 40 months will be allotted to complete study enrollment (~ 5 new subjects/month).

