7.2.3 IN TREATMENT

During the 9-week treatment phase participants will be scheduled to attend three clinic visits per week (MWF). Activities conducted at these visits will include urine testing, administration of study medication, cognitive behavioral therapy, and prize-based CM for attendance. Brief (5-10 min) evaluations by the study nurse will be conducted weekly to address concerns related to side effects, concomitant medications, and general adherence to the medication regimen.

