7.2.4 COMPENSATION SCHEDULE

Participants will receive \$50 for completing the intake assessment phase of this study. Weekly assessments during treatment will take approximately 20 minutes to complete. Participants will earn prize bowl draws each time they attend a clinic visit (MWF) and provide a usable urine specimen. The prize-based CM is explained above (see Sect. 6.5). Behavioral tasks at Weeks -1, 3, 5, 7, and 9 will take approximately 65 minutes to complete. Participants will receive an additional \$25 (gift card) for each of these assessments, plus any task-specific earnings (approx. \$8). Subjects will also receive \$5 for each medication pack returned and bus/parking tokens as needed.

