7.2.5 END OF STUDY VISIT (WEEK 9)

At week 9, participants will be administered end of study assessments and given appropriate referrals to alternative treatment facilities in the area.

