8. ASSESSMENT SCHEDULE

STUDY 64		Admit week	1	2	3	4	5	6	7	8	9	10
Forms												
Study 64 consent form and quiz		X										
Medication information sheet		X										
Weekly Locator		X	X	X	X	X	X	X	X	X	X	X
Con Med		X	X	X	X	X	X	X	X	X	X	X
SUR (3xwk)		X	X	X	X	X	X	X	X	X	X	X
AIMS		X	X	X	X	X	X	X	X	X	X	X
AE		X	X	X	X	X	X	X	X	X	X	X
BDI-2		X										X
BSCS		X										X
SHAPS		X										
URICA		X										
DTCQ		X										
OCDUS		X	X	X	X	X	X	X	X	X	X	X
NART-2		X										
Shipley - 2		X										
Computerized Tests												
IGT-repeat version		X			X		X		X		X	
Risky Decision Making		X			X		X		X		X	
Continuous Performance Test		X			X		X		X		X	
Progressive Ratio (PR)		X			X		X		X		X	
Cocaine Stroop		X			X		X		X		X	
Reversal Learning		X			X		X		X		X	
Activities												
Blood draw				X		X		X		X		X
Preg				X		X		X		X		X
EKG		X		X		X		X		X		X
Vitals		X	X	X	X	X	X	X	X	X	X	X
BAL (3x/wk)		X	X	X	X	X	X	X	X	X	X	X
Urine rapid Test (3x/wk)		X	X	X	X	X	X	X	X	X	X	X
Fishbowl		X	X	X	X	X	X	X	X	X	X	X

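### The documents disagree on whether week 10 is a treatment, assessment and incentive week, and the only BDI-2 and BSCS follow-up falls in it

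*Protocol*

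**What the plan says.** **Treatment length.** The Protocol abstract says "Outpatient treatment will last 10 weeks and consist of thrice-weekly clinic visits". Section 7.2.3 says "During the 9-week treatment phase participants will be scheduled to attend three clinic visits per week (MWF". The SAP (primary hypothesis testing) defines retention as completing 12 weeks.

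**Incentive.** Section 6.5 says "During Treatment, for each visit attended, subjects will earn a draw from the attendance voucher" fishbowl, and adds: "Subjects will earn 5 bonus draws for each week in which all 3 visits in a week" are attended. Table 1 fills in draws for visits 1-27, leaves visits 28-39 blank, and prints "Total: 180 Draws". The compensation section (7.2.4) has no cut-off: "Participants will earn prize bowl draws each time they attend a clinic visit (MWF) and provide a usable urine specimen". The Fishbowl row in section 8 is marked from the admit week through week 10.

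**Assessments.** Section 7.2.5 says "At week 9, participants will be administered end of study assessments". In section 8, BDI-2 and BSCS are marked only at the admit week and week 10. The last blood draw, pregnancy test and EKG are also in week 10. The row "Urine rapid Test (3x/wk") is marked through week 10. The computerized tests end at week 9.

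**Dose.** The section 6.4 tables label week 10 as run-down.

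**The concern.** Some parts of the Protocol treat week 10 as an ordinary week, with visits, urines and draws. Others read as though the study closes at week 9. Three things depend on which reading applies.

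1. BDI-2 and BSCS have one follow-up point. On the schedule, that point is a reduced-dose week after the visit that section 7.2.5 calls the end of study.
2. The primary outcome is a weekly measure of days without cocaine use, and a secondary endpoint is abstinence over the final two treatment weeks. Neither document says whether the run-down week counts, so the secondary window cannot be fixed.
3. If draws stop after week 9, participants lose the attendance reward just as it peaks, while urines are still due three times. Completeness in that week would then be at risk.

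**Working it through.** **Step 1. Reproduce the 180 draws.** In Table 1, week *w* gives *w* draws at each of three visits plus 5 bonus draws, so a fully attended week gives 3*w* + 5.

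- Weeks 1-9: 3 × (1 + 2 + … + 9) + 9 × 5 = 3 × 45 + 45 = 135 + 45 = **180**, as printed.
- Weeks 1-10 with the same escalation: 180 + (10 + 10 + 15) = **215**, which does not match.
- One draw per visit plus the bonus (3 + 5 = 8 a week): 72 over nine weeks or 80 over ten. Neither matches.

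The printed total is therefore a nine-week total, and the blank week 10 cells are not an extraction fault. On Table 1 alone, full attendance earns 9 + 9 + 9 + 5 = 32 draws in week 9 and 0 in week 10.

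**Step 2. Set the passages side by side on week 10.**

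| Source | Week 10 |
|---|---|
| Protocol 1 (abstract) | inside a 10-week treatment |
| Protocol 6.4 | dosed, run-down |
| Protocol 6.5, Table 1 | no draws |
| Protocol 7.2.3 | outside a 9-week treatment phase |
| Protocol 7.2.4 (compensation) | draws at any MWF visit with a usable urine |
| Protocol 7.2.5 | after the end-of-study visit |
| Protocol 8 | urines, Fishbowl, BDI-2, BSCS, blood, pregnancy test, EKG |
| SAP | not mentioned; retention runs to 12 weeks |

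**Step 3. Scheduled daily doses, week 9 to week 10 (section 6.4).**

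| Arm | Levodopa/carbidopa (mg) | Ropinirole (mg) |
|---|---|---|
| Placebo | 0 → 0 | 0 → 0 |
| Levodopa/carbidopa only | 800/200 → 400/100 | 0 → 0 |
| + ropinirole 2 mg | 800/200 → 400/100 | 2 → 0 |
| + ropinirole 4 mg | 800/200 → 400/100 | 4 → 2 |

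Three of four arms change. With 200 participants allocated equally, that is 3 × 50 = 150 by design. In week 10 the levodopa-only and 2 mg arms are both scheduled for 400/100 and 0 mg, so a BDI-2 or BSCS comparison between them would be made while both are on the same scheduled regimen.

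**Step 4. Urines that depend on the answer.**

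- Ten weeks × 3 = 30 scheduled in-treatment urines; week 10 supplies 3/30 = 10%.
- The final two weeks hold 2 × 3 = 6 urines. If these are weeks 9-10, week 10 supplies 3/6 = 50%. If they are weeks 8-9, it supplies none.
- If treatment were 12 weeks, the window would be weeks 11-12, where section 8 schedules nothing.

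**Step 5. Other week 10 items.** Blood draw and pregnancy test are marked at weeks 2, 4, 6, 8 and 10 (five times). EKG is also marked at the admit week (six times). Week 10 is the last mark in each row.

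**The case against.** The best reply is that a coherent nine-week reading exists. Section 6.5 limits draws to the treatment period, section 7.2.3 makes that nine weeks, Table 1 sums to nine weeks, and both the last cognitive battery and the end-of-study visit fall at week 9. Week 10 is then a run-down, and a closing BDI-2 and BSCS at the last contact is a defensible choice. Neither instrument is named as a primary or secondary endpoint, and neither appears in the SAP. For the urines, the reward rule is the same in every blinded arm, and the SAP plans mixed models, with pattern-mixture modelling if differential attrition raises concern.

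Much of this stands, and it keeps the point modest. It does not remove the conflict: the abstract, the compensation section and the assessment schedule all contradict the nine-week reading, and so does the SAP's 12 weeks. Pattern-mixture modelling deals with dropout; it cannot say which weeks form the endpoint window.

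A reader might also infer more than the documents support:

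- **That week 10 data will be missing.** Neither document gives an attendance or dropout figure, so lower completeness is only a risk. A clinic that gave the questionnaires at the week 9 visit would collect them on the maintenance dose.
- **That week 10 attendance is unrewarded.** Only Table 1 says so. Section 7.2.4 and the Fishbowl row say otherwise, and 7.2.4 also pays $5 per returned medication pack and offers travel tokens. The Fishbowl row is itself a loose guide, since it also marks the admit week, which Table 1 does not cover.
- **That every arm is off its assigned dose.** The placebo arm does not change.

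**Conclusion.** The point holds as an unresolved contradiction about week 10, with one avoidable design weakness inside it. As scheduled, the only post-baseline BDI-2 and BSCS are taken after the stated end-of-study visit and at a reduced dose in three of four arms. Two of those arms are then on the same scheduled regimen.

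The effect on named outcomes is definitional: 10% of scheduled urines under a ten-week treatment, and half or none of the final-two-weeks abstinence window. These counts assume three urines a week as scheduled and full attendance. The size of any loss of week 10 data cannot be estimated from the documents. They also do not settle which treatment length is intended, so no particular extension of the draw schedule follows from them.

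**What to change.** 1. **Move the BDI-2 and BSCS follow-up from week 10 to the week 9 end-of-study visit**, beside the last cognitive battery. This agrees with section 7.2.5 and places the single follow-up in a maintenance week under the existing dose tables. The cost is a slightly longer week 9 visit, on top of roughly 65 minutes of behavioral tasks, and no questionnaire data from the run-down week.
2. **Reconcile treatment length** across the abstract, section 7.2.3, section 7.2.5, section 8 and the SAP's retention definition.
3. **State whether week 10 visits earn draws.** If they do, complete Table 1 and correct its total. If they do not, limit the rule in section 7.2.4 and the Fishbowl row to match.
4. **Reconcile sections 7.2.5 and 8** on the week of the closing blood, pregnancy and EKG checks.
5. **State in the SAP** whether week 10 urines enter the weekly primary outcome, and name by number the two weeks that define the abstinence endpoint, before unblinding.

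Items 2 to 5 are edits to the text, apart from the prize cost if draws are extended. The documents do not give the full mix of slip values, so that cost cannot be fixed from them.
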